7.2 Exclusion Criteria

Any subject who meets any of the following criteria will not qualify for entry into the study:

1. The subject has muscular pain secondary to acute trauma or fractures (e.g., due to osteoporosis). Such conditions could have been ruled out based on medical history, x-ray, or physical examination.
2. The subject suffers from muscle spasms/pain related to polymyalgia rheumatica or ankylosing spondylitis (Bekhterev's disease). Such conditions could have been ruled out based on medical history, x-ray, or physical examination;
3. The subject has received any investigational compound within 30 days prior to Screening.
4. If female, the subject is pregnant or lactating or intending to become pregnant before, during, or within 1 month after participating in this study; or intending to donate ova during such time period.

5. The subject has a history of drug abuse or recent (within the last 12 months) history of excessive alcohol consumption defined as >2 drinks/day (>3 oz of 80 proof alcohol or equivalent).
6. Patients with mild, moderate, severe liver impairment.
7. The subject is an immediate family member, study site employee, or is in a dependent relationship with a study site employee who is involved in conduct of this study (eg, spouse, parent, child, sibling) or may consent under duress.
8. The subject takes any concomitant medication including over-the-counter and herbal products for muscle spasms. If a subject is taking such medications, the medications has to be discontinued before starting the study.
9. The subject takes or took within last 14 days medications, such as:
 - a. selective serotonin reuptake inhibitors (SSRIs);
 - b. serotonin norepinephrine reuptake inhibitors (SNRIs);
 - c. tricyclic antidepressants (TCAs);
 - d. MAO inhibitors;
 - e. tramadol;
 - f. bupropion;
 - g. meperidine;
 - h. verapamil; topical anti-inflammatory medications, including patches
 - i. paracetamol
 - j. opioid analgesics
10. The subject takes or took within last 3 days medications, such as:
 - a. non-steroid anti-inflammatory drugs (NSAIDs);
 - b. Intramuscular vitamin injections containing anaesthetics (such as vitamin Milgamma).
11. The subject has a history or clinical manifestations of significant medical condition, such as:
 - a. hyperthyroidism;
 - b. acute recovery phase of myocardial infarction;
 - c. arrhythmias, heart block or conduction disturbances;
 - d. congestive heart failure;
 - e. angle-closure glaucoma;
 - f. urinary retention;
 - g. increased intraocular pressure.
12. The subject has abnormal physical findings or a medical condition that might have placed the subject at risk or interfered with the subject's ability to participate in the study.

13. The subject has any known condition or disorder that might have affected absorption of the study drug.
14. The subject has a history of hypersensitivity or allergies to cyclobenzaprine and/or tricyclic antidepressants or any of their components.
15. The subject has a history of hypersensitivity to any NSAIDs including salicylate sensitivity.
16. The subject has a history of thrombocytopenia.
17. The subject has a history of gastro-intestinal bleeding, cerebrovascular bleeding or other bleeding disorders.
18. The subject had active or history of recurrent peptic ulcer/haemorrhage (two or more distinct episodes of proven ulceration or bleeding)
19. The subject has a history of severe renal impairment
20. The subject had a major surgery during the 6 months preceding study entry.
21. The subject has a language barrier or any other problems precluding good communication or cooperation.
22. The subject has any reason to believe that he/she would not be able to complete the evaluations needed in this study.
23. The subject has a known history of positive screen for hepatitis B surface antigen, hepatitis C antibody, or human immunodeficiency virus (HIV) antibody.
24. The subject has a history of malignant disease within 5 years prior to Screening.
25. Drug abuse in anamnesis

7.3 Excluded Medications and Treatments

Drug Class	Disallowed Prior to Screening	Disallowed During the Study for		
		Chronic Use	Episodic Use	Comments or Exceptions
Analgesics				Concomitant use of Cyclobenzaprine with listed medications can lead to a potentially life-threatening serotonin syndrome and /or affect the study results.
• tramadol	14 days	+	+*	
• meperidine	14 days	+	+*	
• paracetamol	14 days	+	+*	
• opioid analgesics	14 days	+	+*	
Antiarrhythmics				
• verapamil	14 days	+	+	

Antidepressants 
 • selective serotonin reuptake inhibitors • serotonin norepinephrine reuptake inhibitors • tricyclic antidepressants • MAO inhibitors • Bupropion 	14 days	+	+	
	14 days	+	+	
	14 days	+	+	
	14 days	+	+	
	14 days	+	+	

 • Topical anti-inflammatory medications (including patches) 	14 days	+	+*	

 • NSAIDs • intramuscular vitamin injections containing anaesthetics (such as Milgamma) 	3 days	+	+*	
	3 days	+	+	

*Analgesics will be allowed only as add-on rescue therapy, to be used before the subject is discontinued due to lack of efficacy.

Subjects will be instructed not to take any medications, including over-the-counter products, without first consulting with the investigator.

Medications necessary for the well-being of the subject will be allowed during the study.

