6.2 Justification for Study Design, Dose, and Endpoints

- Study design including primary and secondary criteria for evaluation and methods of measurement will be similar to previous pivotal Cyclobenzaprine studies in order to determine positive efficacy trend of Cyclobenzaprine 15 mg versus Placebo;
- The randomized, double-blind, parallel, placebo-controlled design will reduce bias in different treatment regimens with respect to efficacy and safety. Randomization will provide maximum assurance that subject characteristics are similar across the treatment groups. Blinding subjects and all study personnel who will be involved in their assessment to the study treatment will maintain the objectivity of the assessment;
- A placebo arm has been added, since the primary endpoint is a subjective score and the placebo control allows to better evaluate the treatment effect of Cyclobenzaprine;
- A placebo arm is acceptable because the study is of short duration and the cervical and/or lower back pain due to muscle spasms is not considered a life-threatening condition if untreated. Moreover, rescue therapy will be implemented in lack of efficacy cases before subject is discontinued from the study;
- The dose level of Cyclobenzaprine 15 mg once daily is chosen for this study as the approved dose for the treatment of the pain due to muscle spasms of local origin. The Cyclobenzaprine 15 mg once daily has shown its efficacious and safe in adult patients with the pain due to muscle spasms, so it is expected that the same dose will be effective and safe in Russian patients.

The endpoint assessment for this study will take place on Day 3 instead of Day 4 (as utilized in 1105 and 1106 studies) which is based on cyclobenzaprine MR 30 mg pharmacokinetic parameters T_{max}

= 10.5 ± 3.32 hours and $t_{1/2} = 27.7 \pm 8.56$ hours and implies capturing probable earlier clinical effects of the drug than it was shown in previous studies.

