Note: If the subject is found to be pregnant, the subject must be withdrawn immediately. The procedure is described in Section 9.1.11.

7. Lack of efficacy. The necessity to use rescue medication (any analgesics) AND/OR the investigator has determined that the subject is not benefiting from investigational treatment and, continued participation would pose an unacceptable risk to the subject.

8. Other.

Note: The specific reasons should be recorded in the "specify" field of the (e)CRF.

CONFIDENTIAL

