7.6 Procedures for Discontinuation or Withdrawal of a Subject

The investigator may discontinue a subject's study participation at any time during the study when the subject meets the study termination criteria described in Section 7.5. In addition, a subject may discontinue his or her participation without giving a reason at any time during the study. Should a subject's participation be discontinued, the primary criterion for termination must be recorded by the investigator. In addition, efforts should be made to perform all procedures scheduled for the Early Termination Visit. Discontinued or withdrawn subjects will not be replaced.

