8.1.1.2 Rescue Medication

NSAIDs, topical over-the-counter medications and other analgesics will be allowed as rescue therapy only and to be used before the subject is discontinued due to lack of efficacy.

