Due to structural similarity with tricyclic antidepressants, cyclobenzaprine can pose a threat to life when interacting with MAO inhibitors. In patients taking cyclobenzaprine concurrently with MAO inhibitors hyperthermic episodes and seizures have also been observed.

The drug can intensify effect of ethanol, barbiturates and other drug products inhibiting CNS; increase the risk of seizures in patients taking tramadol. The drug can block antihypertensive effect of guanethidine and in the same way acting compounds.

Cases of serotonin syndrome have been reported during coadministration of cyclobenzaprine with other drug products, such as selective serotonin reuptake inhibitors (SSRI), selective serotonin noradrenaline reuptake inhibitors (SNRI), tricyclic antidepressants, tramadol, bupropion, trimeperidine, verapamil or MAO inhibitors (ref. to *Special Precautions* Section).

Special precautions

Considering similar pharmacological effect of cyclobenzaprine with other drug products of tricyclic structure, consider probability of withdrawal syndrome with administration of Myorix®, despite that fact that similar cases for this drug have not been registered. Sharp treatment cessation after long period of administration can cause nausea, headache and sickness.

In case of suspected hypersensitivity response (ref. to *Side Effect* Section) stop administration of Myorix®.

Myorix® should be used only during a short period (up to two-three weeks), as long as data on the drug efficiency with longer administration are unavailable, and also due to that fact, that muscle spasm, related to locomotor system disorders usually has short duration and specific treatment for more than three weeks is rarely reasonable.

It was found that Myorix® is not efficient for treatment of muscle spasms induced by disorders of central nervous system or cerebral palsy in children (ref. to *Indications* Section).

Serotonin syndrome

In case of administration of cyclobenzaprine in combination with other drug products (ref. to *Drug-to-drug interaction* Section) there are reports on potentially life threatening serotonin syndrome. Serotonin syndrome symptoms manifest in the form of mental change (e.g., confused consciousness, high excitation, hallucinations), autonomic nervous system instability (e.g., diaphoresis (diaphoresis), tachycardia, unstable arterial pressure, hyperthermia), disturbed

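### Sections 7.3 and 8.1.1.2 permit tramadol and meperidine as rescue on top of blinded study drug, although Appendix E names tramadol for serotonin syndrome and seizures

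*Protocol*

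**What the plan says.** Protocol Section 7.3 lists tramadol, meperidine, paracetamol and opioid analgesics under analgesics. Each is barred for 14 days before screening and disallowed during the study, but the episodic-use mark carries an asterisk. The footnote to it reads: "Analgesics will be allowed only as add-on rescue therapy, to be used before the subject is discontinued due to lack of efficacy". The comment column of the same table warns: "Concomitant use of Cyclobenzaprine with listed medications can lead to a potentially life-threatening serotonin syndrome", and adds that the listed drugs may also, or instead, affect the results.

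Section 8.1.1.2 says: "NSAIDs, topical over-the-counter medications and other analgesics will be allowed as rescue therapy only". It sets no exception for any analgesic. Section 6.2 gives the order of events: "rescue therapy will be implemented in lack of efficacy cases before subject is discontinued from the study". Section 7.5, item 7, opens its definition of lack of efficacy with "The necessity to use rescue medication (any analgesics", so rescue is not restricted there either. Section 7.6 then leaves the act of discontinuing to judgement: "The investigator may discontinue a subject's study participation at any time during the study".

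Appendix E (drug-to-drug interaction) reports serotonin syndrome with SSRIs, SNRIs and a further group: "tricyclic antidepressants, tramadol, bupropion, trimeperidine, verapamil or MAO inhibitors". It separately reports a raised seizure risk in patients taking tramadol. Its section on serotonin syndrome accepts serotonergic co-treatment where clinically reasonable, recommends thorough monitoring, and says to stop both drugs at once if reactions occur.

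**The concern.** Rescue that is added on, and given before discontinuation, is given while the subject is still taking blinded capsules. For tramadol, and less certainly for meperidine, the Protocol thus authorises a combination that its own drug information describes as hazardous. The investigator does not know whether the subject is on CER or placebo when choosing the rescue drug.

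The issue is subject safety, not inference. The risk is also avoidable, because NSAIDs, paracetamol and topical products are already allowed as rescue. Permitted and prohibited medication is set by the protocol and not by an analysis plan, so this is the document in which to settle it.

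**Working it through.** The plan states no figure on this point to reproduce. The check compares the lists.

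**Step 1. Which rows carry the rescue exception (Section 7.3).** The table has 4 analgesic + 1 antiarrhythmic + 5 antidepressant + 1 topical + 2 further rows (NSAIDs, intramuscular vitamins) = 13. The asterisk is on the 4 analgesic rows, the topical row and the NSAID row: 4 + 1 + 1 = 6.

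**Step 2. The Appendix E serotonin-syndrome list against Section 7.3.**

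| Appendix E entry | Mark for episodic use in 7.3 |
|---|---|
| SSRIs | banned, no exception |
| SNRIs | banned, no exception |
| Tricyclic antidepressants | banned, no exception |
| Bupropion | banned, no exception |
| Verapamil | banned, no exception |
| MAO inhibitors | banned, no exception |
| Tramadol | banned, but allowed as rescue |
| Trimeperidine | not named; allowed as rescue if counted as an opioid analgesic |

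Six of the eight entries are closed without exception. Tramadol is open by name. Trimeperidine is open through the opioid row, on the assumption that it counts as an opioid analgesic. Meperidine is open by name in 7.3 but is not on the Appendix E list. Its case rests on the general 7.3 comment and on an assumed similarity to trimeperidine.

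**Step 3. Does another section withdraw the permission?** Section 8.1.1.2 has no exclusion, 7.5 item 7 covers any analgesic, and 6.2 puts rescue before discontinuation. No section requires study drug to stop before either drug is given. The rescue text sets no monitoring, and clinic visits are scheduled on Days 3, 7 and 15, so rescue after Day 7 could fall in a gap of 15 − 7 = 8 days.

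**Step 4. Who could be exposed.** Allocation is 1:1, with 90 of 180 on CER, so 90/180 = 50% could have cyclobenzaprine on board. The documents give no rescue rate and no share for tramadol or meperidine, so the count cannot be taken further.

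**Step 5. Is drug still present in the CER arm after a dose?** Assume simple exponential decline, with the Appendix E half-life of 32 h (range 8 to 37 h). Fraction left = 0.5^(t / half-life).

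- 24 h, 32 h half-life: 0.5^(24/32) = 0.595, about 59%
- 24 h, 8 h half-life: 0.5^(24/8) = 0.125, about 13%
- 24 h, 37 h half-life: 0.5^(24/37) = 0.638, about 64%
- 48 h, 32 h half-life: 0.5^(48/32) = 0.354, about 35%

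This shows only that cyclobenzaprine remains present a day or two after a capsule. It does not measure the risk of serotonin syndrome or seizure.

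**The case against.** The other side has a fair case.

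- **Physician control.** Section 7.3 tells subjects to take nothing without first consulting the investigator, and 8.1.1.1 refers to Appendix E as the detailed drug information, so its advice on monitoring and stopping is available. This reduces the risk, but the investigator would be following a table that marks these drugs as permitted.
- **Short overlap.** Need for rescue is itself a lack-of-efficacy discontinuation reason, and 7.6 treats the 7.5 list as termination criteria. This stands: the plan describes rescue on the way out, not continued co-treatment. It limits the exposure but does not remove the permission.
- **No label breach.** A reader might infer that the Protocol allows a contraindicated combination. It does not: among co-medications, Appendix E contraindicates only MAO inhibitors.
- **The 14-day bar.** A reader might take the exclusion that begins "The subject takes or took within last 14 days medications, such as" as proof that the sponsor saw a serotonin hazard in every drug on it. The same bar covers paracetamol and topical anti-inflammatory products, and the 7.3 comment gives effect on the results as another reason. The bar alone proves little.
- **Meperidine.** A reader might treat both drugs as equally documented. Only tramadol is named in Appendix E.
- **Drug on board.** A reader might infer that every such rescue meets circulating cyclobenzaprine, or that the half-life figures size the danger. The first is untrue for the placebo arm, and the figures show persistence only.

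**Conclusion.** The point holds for tramadol on drug-specific evidence in the Protocol's own appendix, and for meperidine on weaker, partly assumed grounds. The plan closes six of the eight Appendix E serotonin-syndrome entries without exception and leaves tramadol open as add-on rescue; trimeperidine is probably open too, through the opioid row. Nothing elsewhere in the Protocol withdraws that permission.

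The size is limited and partly unknown. Only CER subjects, about half, can be affected; the intended overlap is short; and the number exposed cannot be computed. The conclusion assumes that the asterisk means what its footnote says, that trimeperidine falls under opioid analgesics, and, for meperidine, that it behaves like trimeperidine. The change should be made, because the named harm is potentially life-threatening and the alternatives are already allowed. Confidence is medium.

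**What to change.** - **Section 7.3:** remove the asterisk from tramadol and meperidine. For opioid analgesics, either remove it as well (6 − 3 = 3 starred rows remain) or keep it and state that opioid rescue excludes tramadol, meperidine and trimeperidine (6 − 2 = 4 remain).
- **Section 8.1.1.2:** replace the open reference to other analgesics with a named list that matches 7.3: NSAIDs, paracetamol and topical products, plus non-serotonergic opioids only if the opioid row keeps its asterisk.
- **Section 7.5, item 7:** keep use of any analgesic as a discontinuation reason, but refer to 8.1.1.2 for what is permitted as rescue.
- **Section 7.3, medically necessary drugs:** the table's closing text allows medications needed for the subject's well-being and could readmit the excluded drugs. State that, if one of them is necessary, study drug is stopped and the subject is monitored as Appendix E advises. Monitoring matters as well as stopping, since cyclobenzaprine persists after the last capsule.

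The cost is one amendment with IRB/IEC approval (Appendix B, item 5), site training and a slightly narrower rescue choice. Sample size and planned analyses are unaffected.

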7.5 Criteria for Discontinuation or Withdrawal of a Subject

The primary reason for discontinuation or withdrawal of the subject from the study or study medication should be recorded in the case report form ([e]CRF) using the following categories. For screen failure subjects, refer to Section 9.1.12.

1. Pretreatment event (PTE) or adverse event (AE). The subject has experienced a PTE or AE that requires early termination because continued participation imposes an unacceptable risk to the subject's health or the subject is unwilling to continue because of the PTE or AE.

- Liver Function Test (LFT) Abnormalities

Study medication should be discontinued immediately with appropriate clinical follow-up (including repeat laboratory tests, until a subject's laboratory profile has returned to normal/baseline status, see Section 9.1.9), if the following circumstances occur at any time during study medication treatment:

- alanine aminotransferase (ALT) or aspartate aminotransferase (AST) $>8 \times$ upper limit of normal (ULN), or
- ALT or AST $>5 \times$ ULN and persists for more than 2 weeks, or
- ALT or AST $>3 \times$ ULN in conjunction with elevated total bilirubin $>2 \times$ ULN or international normalized ratio (INR) >1.5 , or
- ALT or AST $>3 \times$ ULN with appearance of fatigue, nausea, vomiting, right upper quadrant pain or tenderness, fever, rash and/or eosinophilia ($>5\%$).

2. Significant protocol deviation. The discovery postrandomization that the subject failed to meet protocol entry criteria or did not adhere to protocol requirements, and continued participation poses an unacceptable risk to the subject's health.
3. Lost to follow-up. The subject did not return to the clinic and attempts to contact the subject were unsuccessful. Attempts to contact the subject must be documented.
4. Voluntary withdrawal. The subject (or subject's legally acceptable representative) wishes to withdraw from the study. The reason for withdrawal, if provided, should be recorded in the (e)CRF.

Note: All attempts should be made to determine the underlying reason for the withdrawal and, where possible, the primary underlying reason should be recorded (ie, withdrawal due to an AE or lack of efficacy).

5. Study termination. The sponsor, IRB, IEC, or regulatory agency terminates the study.
6. Pregnancy. The subject is found to be pregnant.

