8.5 Unblinding Procedure

The investigational drug blind shall not be broken by the investigator unless information concerning the investigational drug is necessary for the medical treatment of the subject. In the event of a medical emergency, if possible, the medical monitor should be contacted before the investigational drug blind is broken to discuss the need for unblinding.

For unblinding a subject, the investigational drug blind can be obtained by the investigator, by accessing the IVRS/IWRS.

The sponsor must be notified as soon as possible if the investigational drug blind is broken. The date, time, and reason the blind is broken must be recorded in the source documents and the same information (except the time) must be recorded on the (e)CRF.

If any site personnel are unblinded, investigational drug must be stopped immediately and the subject must be withdrawn from the study.

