Cyclobenzaprine to a great degree is metabolized and excreted primarily in the form of glucuronides by urinary way. Cytochrome isoenzymes P-450 3A4, 1A2, and to a lesser degree, 2D6, mediate N-demethylation - one of oxidation ways of cyclobenzaprine metabolism. Elimination half-time of cyclobenzaprine - 32 hours (8- 37 hours range; n = 18); total body clearance - 0.7 L/min after single drug dose administration.

Elderly patients (65 years old and over)

Despite that fact, that no significant difference in C_{max} or T_{max} has been observed, AUC of plasma cyclobenzaprine increased to 40%, cyclobenzaprine elimination half-time was longer in elderly patients at the age of 65 years and more (50 hours) compared to younger patients at the age of 18 -45 years (32 hours). Pharmacokinetics of cyclobenzaprine after multiple dose administration of drug in elderly patients was not evaluated.

Patients with liver function abnormality

In pharmacokinetics study of cyclobenzaprine immediate release in 16 patients with liver dysfunction (15 slight, 1 moderate based on Child – Pugh scores), both AUC, and C_{max} were approximately twice higher compared to values in healthy control group. Pharmacokinetics of cyclobenzaprine in patients with severe liver dysfunction has not been observed.

Indications for use:

Myorix® is indicated as therapeutic appliance for acute pain control in case of muscle spasm, induced by disorders of locomotor system. Drug effect is based on elimination of muscle spasm and its symptoms, i.e. pain syndrome and limited excursion.

Myorix® should be used only during a short period (up to two-three weeks), as long as data on the drug efficiency with longer administration are unavailable, and also due to that fact, that muscle spasm, related to locomotor system disorders usually has short duration and specific treatment for more than three weeks is rarely reasonable.

It was found that Myorix® is not efficient for treatment of muscle spasms induced by disorders of central nervous system, and also with cerebral palsy in children.

Contra indications:

- hypersensitivity to cyclobenzaprine or other drug components;
- children under 18 years;
- coadministration with monoaminooxidase inhibitors (MAO) and administration within 14 days after their withdrawal.
- recent myocardial infarction, fibrillation, AV block or other asequences, congestive heart failure, unstable angina;
- hyperthyroidism.

Administration during pregnancy and breastfeeding

Pregnancy

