neuromuscular transmission (e.g., tremor, ataxia, hyperreflexia, myoclonus, rigid muscles), gastrointestinal disorders (e.g., nausea, vomiting, diarrhea). In case the above reactions take place, immediately stop treatment with Myorix® and any associated serotonergic medicinal product and start symptomatic treatment. If associated treatment with Myorix® and other serotonergic medicinal products is clinically reasonable, it is recommended to provide thorough monitoring, especially during the beginning of therapy or dose increase.

Effects, similar to effects of tricyclic antidepressants.

Cyclobenzaprine has similar structure with tricyclic antidepressants (amitriptyline, imipramine). There are registered reports that tricyclic antidepressants cause heart rhythm disorder, sinus tachycardia, increased conduction time based on cardiac conduction system, which may lead to myocardial infarction or stroke (ref. to *Contraindications* Section).

Some of more serious reactions of CNS, observed in tricyclic antidepressants, were observed also in studies of cyclobenzaprine use for other indications and usually in doses far exceeding doses recommended for use in case of skeletal muscle spasms. In case of clinically significant symptoms of effect on CNS, consider possibility to withdraw treatment with Myorix®.

Elderly patients

It is not recommended to use Myorix® in elderly patients due to increase of cyclobenzaprine content in plasma to 40 % and increase of elimination half-time to 56 % after administration of the drug by elderly patients compared to younger patients.

Patients with liver function abnormality

It is not recommended to use Myorix® in patients with slight, moderate or severe liver dysfunction due to double increase of cyclobenzaprine content in plasma in patients with slight liver dysfunction compared to patients without liver dysfunction due to limited possibility of drug dose change.

Atropine-like action

Prescribe Myorix® with care to patients with data on urinary retention, angle-closure glaucoma, elevated intraocular pressure in medical history, and in patients taking anticholinergic drugs due to atropine-like action of cyclobenzaprine.

Effects on ability to drive and use machines

Pursuant to adverse reactions profile, it is recommended to abstain from activity, requiring high alertness and promptness of psychomotor reaction, e.g., driving vehicles or working with machines and mechanisms.

Presentation

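### The closing sentence of Section 7.3 lacks a qualifier and, read literally, undoes the table's unconditional bans on six interacting drugs; no rule requires study drug to stop even for MAO inhibitors

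*Protocol*

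**What the plan says.** Protocol Section 7.3 tabulates drugs disallowed before screening and during the study. Verapamil, SSRIs, SNRIs, tricyclics, MAO inhibitors, bupropion and intramuscular vitamin injections with anaesthetic are marked as disallowed for both chronic and episodic use, with no asterisk. The asterisk on other rows permits analgesics as rescue only. The comments column gives the reason: "Concomitant use of Cyclobenzaprine with listed medications can lead to a potentially life-threatening serotonin syndrome", or an effect on the results. Two general sentences follow. The first tells subjects to consult the investigator before taking anything. The last reads: "Medications necessary for the well-being of the subject will be allowed during the study".

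Appendix E (the product leaflet) bears on this in three places:

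- Its interaction section lists drugs with reported serotonin syndrome: SSRIs and SNRIs, followed by "tricyclic antidepressants, tramadol, bupropion, trimeperidine, verapamil or MAO inhibitors".
- Its contraindications include "coadministration with monoaminooxidase inhibitors (MAO) and administration within 14 days after their withdrawal".
- Its precautions order a stop after symptoms ("In case the above reactions take place, immediately stop treatment with Myorix® and any associated serotonergic medicinal product") but accept co-treatment in some cases: where use with "other serotonergic medicinal products is clinically reasonable, it is recommended to provide thorough monitoring".

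**The concern.** The closing sentence does not say that it covers only other drugs, and no section ranks it against the table. An investigator who follows it as written could start one of the listed drugs because the subject needs it and leave the subject on blinded capsules, which contain cyclobenzaprine in one of two equally allocated arms. Section 7.3 itself describes that kind of combination as potentially life-threatening.

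The second part concerns what happens next. Pregnancy, liver-test thresholds and unblinding each carry an explicit instruction to stop study drug. Starting an interacting drug does not. For MAO inhibitors this leaves a contraindicated combination without a matching stopping rule in the body of the protocol. What is at stake is the safety of a small number of subjects, not the efficacy result.

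**Working it through.** No power or alpha figure is involved. The check is a count and a comparison of texts.

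**1. Rows affected.** Section 7.3 has 13 entries.

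- With an asterisk (6): tramadol, meperidine, paracetamol, opioid analgesics, topical anti-inflammatories, NSAIDs.
- Without (7): verapamil, SSRIs, SNRIs, tricyclics, MAO inhibitors, bupropion, intramuscular vitamin injections.

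Of the 7, the injections are absent from the Appendix E interaction list, so 7 − 1 = 6 are relevant to safety. Of those 6, one (MAO inhibitors) is contraindicated in Appendix E and 6 − 1 = 5 are not. The six can be matched to Appendix E by name, so the count does not depend on which table rows the comment was meant to span.

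**2. Is there a required stop when one of the six is started?**

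| Provision | What triggers it | Required stop on starting the drug? |
|---|---|---|
| 7.5 item 1 | An event, plus unacceptable risk or the subject's unwillingness to continue | No |
| 7.5 item 2 | The subject "did not adhere to protocol requirements, and continued participation poses an unacceptable risk to the subject's health" | No; needs a risk judgement |
| 7.5 item 7 | Rescue analgesics, or no benefit with unacceptable risk | No |
| 7.5 item 8 | Other reasons | No |
| 7.6 | The investigator may discontinue | No |
| 8.5 | Blind kept "unless information concerning the investigational drug is necessary for the medical treatment of the subject"; study drug stops once site staff are unblinded | Only if the investigator chooses to unblind |
| 14.2 | Do not deviate; consult the sponsor; notify significant deviations | No; consultation |
| Appendix E precautions | Symptoms of serotonin syndrome | Only after symptoms appear |

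No provision requires a stop, for MAO inhibitors or for the other five.

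**3. The safeguards depend on the same ambiguity.** Item 2 of Section 7.5 (non-adherence) and Section 14.2 (deviation) apply if the table governs. If the closing sentence governs, the drug is permitted, and its use is arguably neither non-adherence nor a deviation. The default is then the instruction in Section 9.3.2 to take study drug for the full 14 days.

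**4. Expected number.** The documents give no rate of new starts. Assume 0 to 4 among 180 subjects: 4/180 = 2.2%. With 1:1 allocation, 4 × 1/2 = 2, so about 0 to 2 subjects would be co-exposed to cyclobenzaprine. Treatment lasts 14 days, and Section 7.2 excludes users of these drugs in the preceding 14 days and subjects with arrhythmia. These features favour the low end.

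**5. What a stop achieves.** The half-life is 27.7 h in Section 6.2 (30 mg capsule) and 32 h in Appendix E. Assuming first-order decline, the fraction left after 24 h is 2^(−24/27.7) = 0.55 to 2^(−24/32) = 0.59. Five half-lives take 5 × 27.7 = 138.5 h (5.8 days) to 5 × 32 = 160 h (6.7 days). Stopping on the day the new drug starts therefore leaves several days of overlap.

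**The case against.** In context, the sentence closes a section on excluded medications, and specific prohibitions ordinarily govern a general closing line. Read the other way, the table would bar almost nothing that a subject needed. That is the more natural reading, and it stands. A reader might infer that the protocol deliberately permits these combinations; the documents do not support that. What they contain is an ambiguity.

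On the natural reading, Section 14.2 does real work. The investigator should not deviate except to remove an immediate hazard, and should consult the sponsor on the course of action if a deviation becomes necessary. Concomitant medication is asked about at every visit. A newly needed antidepressant may also reflect a new or worsened condition that counts as an adverse event under Section 10.1.3, which opens item 1 of Section 7.5. These points stand as partial protection: they lead to consultation and judgement, not to a stop.

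A reader might also infer that study drug must be stopped for all six drugs. Appendix E does not support this. It contraindicates only MAO inhibitors and accepts clinically reasonable serotonergic co-treatment with monitoring. A compulsory stop for the other five would be stricter than the product information and is a trade-off. Two limits on the leaflet's tolerance remain: it does not override the MAO inhibitor contraindication, and Section 7.3 provides for no such monitoring in subjects whose treatment is blinded.

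**Conclusion.** The point holds as a defect of wording with a safety consequence. The closing sentence of Section 7.3 literally contradicts six unconditional, safety-relevant entries in the table above it, and no rule requires study drug to stop even for the one class that Appendix E contraindicates. The likely intent is unlisted drugs only, and Sections 14.2 and 7.5 give partial cover on that reading.

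The size is small: about 0 to 2 co-exposed subjects, resting on an assumed 0 to 4 new starts that has no source in the documents and could be zero. Efficacy, power and alpha are essentially unaffected. Nor should it be inferred that a stopping rule would abolish the risk, because the half-life leaves overlap for days. The weight is minor to moderate. The change is worth making because the possible harm is serious and the repair is nearly free.

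**What to change.** Replace the closing sentence of Section 7.3 with text to this effect:

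*Other medications, not listed above, may be given during the study when the subject's well-being requires them. If an MAO inhibitor becomes necessary, study drug must be stopped before it is started (see Section 7.5). If verapamil, an SSRI, an SNRI, a tricyclic or bupropion becomes necessary, the investigator must contact the sponsor's medical monitor before it is started to decide whether study drug is stopped. If study drug continues, the subject is monitored for serotonin syndrome.*

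The discussion with the medical monitor should cover when the new drug is started, given the remaining exposure shown above. The intramuscular injections stay prohibited, and their use is handled as a deviation under Section 14.2. Stops can be recorded under the existing item 8 of Section 7.5.

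The cost is a few sentences, a cross-reference and at most a very few extra discontinuations. Even if all of the assumed 0 to 4 subjects stopped, that compares with a planned allowance of 180 − 154 = 26. The carry-forward rule in Section 13.1.3 already covers them, and only stops before the Day 3 rating could touch the primary endpoint. No scheduled visit, analysis method or sample size changes.
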